### **8.4      Warnings and precautions**

No evidence available at the time of the approval of this study protocol indicated that special warnings or precautions were appropriate, other than those noted in the provided [Investigator Brochure]. Additional safety information collected between IB updates will be communicated in the form of Investigator Notifications. This information will be included in the patient informed consent and should be discussed with the patient during the study as needed.

### **8.5      Data Monitoring Committee**

A Data Monitoring Committee will not be used for this trial.

## **8.6      Steering Committee**

The steering committee will be established comprising investigators participating in the trial and Novartis representatives from the Clinical Trial Team.

The SC will ensure transparent management of the study according to the protocol through recommending and approving modifications as circumstances require. The SC will review protocol amendments as appropriate. Together with the clinical trial team, the SC will also develop recommendations for publications of study results including authorship rules. The details of the role of the Steering Committee will be defined in a Steering Committee charter.

# **9       Data collection and management**

## **9.1      Data confidentiality**

Information about study subjects will be kept confidential and managed under the applicable laws and regulations. Those regulations require a signed subject authorization informing the subject of the following:

- What protected health information (PHI) will be collected from subjects in this study
- Who will have access to that information and why
- Who will use or disclose that information
- The rights of a research subject to revoke their authorization for use of their PHI.

In the event that a subject revokes authorization to collect or use PHI, the investigator, by regulation, retains the ability to use all information collected prior to the revocation of subject authorization. For subjects that have revoked authorization to collect or use PHI, attempts should be made to obtain permission to collect follow-up safety information (e.g. has the subject experienced any new or worsened AEs) at the end of their scheduled study period.

The data collection system for this study uses built-in security features to encrypt all data for transmission in both directions, preventing unauthorized access to confidential participant information. Access to the system will be controlled by a sequence of individually assigned user identification codes and passwords, made available only to authorized personnel who have completed prerequisite training.

## **9.2      Site monitoring**

Before study initiation, at a site initiation visit or at an investigator's meeting, Novartis personnel (or designated CRO) will review the protocol and CRFs with the investigators and their staff. During the study, the field monitor will visit the site regularly to check the completeness of patient records, the accuracy of entries on the CRFs, the adherence to the protocol to Good Clinical Practice, the progress of enrollment, and to ensure that study treatment is being stored, dispensed, and accounted for according to specifications. Key study personnel must be available to assist the field monitor during these visits.

The investigator must maintain source documents for each patient in the study, consisting of case and visit notes (hospital or clinic medical records) containing demographic and medical information, laboratory data, electrocardiograms, and the results of any other tests or

assessments. All information recorded on CRFs must be traceable to source documents in the patient's file. The investigator must also keep the original signed informed consent form (a signed copy is given to the patient).

The investigator must give the monitor access to all relevant source documents to confirm their consistency with the CRF entries. Novartis monitoring standards require full verification for the presence of informed consent, adherence to the inclusion/exclusion criteria and documentation of SAEs. Additional checks of the consistency of the source data with the CRFs are performed according to the study-specific monitoring plan.

### **9.3 Data collection**

For studies using Electronic Data Capture (EDC), the designated investigator staff will enter the data required by the protocol into the Electronic Case Report Forms (eCRF). The eCRFs have been built using fully validated secure web-enabled software that conforms to 21 CFR Part 11 requirements. Investigator site staff will not be given access to the EDC system until they have been trained. Automatic validation programs check for data discrepancies in the eCRFs and allow modification or verification of the entered data by the investigator staff.

The Principal Investigator is responsible for assuring that the data entered into eCRF is complete, accurate, and that entry and updates are performed in a timely manner.

### **9.4 Database management and quality control**

For studies using eCRFs, Novartis personnel (or designated CRO) will review the data entered by investigational staff, including data from the Oral Stomatitis Daily Questionnaires, for completeness and accuracy. Electronic data queries stating the nature of the problem and requesting clarification will be created for discrepancies and missing values and sent to the investigational site via the EDC system. Designated investigator site staff are required to respond promptly to queries and to make any necessary changes to the data.

Concomitant treatments and prior medications entered into the database will be coded using the WHO Drug Reference List, which employs the Anatomical Therapeutic Chemical classification system. Medical history/current medical conditions and adverse events will be coded using the Medical dictionary for regulatory activities (MedDRA) terminology.

For EDC studies, after database lock, the investigator will receive a CD-ROM or paper copies of the patient data for archiving at the investigational site.

## **10 Statistical methods and data analysis**

The data analysis will be performed by Novartis and/or a designated CRO. It is planned that the data from all centers participating in the trial will be combined, so that an adequate number of patients are available for analysis. Any data analyses performed independently by any investigator should be submitted to Novartis before publication or presentation.

## **10.1 Analysis sets**

### **10.1.1 Full Analysis Set**

The primary efficacy population is defined as the Full Analysis Set (FAS), which consists of all patients to whom the first line study treatment has been assigned. All primary efficacy analyses will be evaluated based on data from this population.

For second line efficacy analyses a subset of the FAS will be used and referred to as Full Analysis Set 2nd line (FAS-2L), which consists of all patients in the FAS who received at least one dose of 2nd line study medication.

### **10.1.2 Safety Set**

The Safety Population includes all patients who received at least one dose of study medication and had at least one post-baseline safety assessment.

The safety analysis for the second line will be performed on the subset of patients receiving at least one dose of second line medication. This subset will be referred to as Safety Population 2nd line (Safety 2L). Note: the statement that a patient had no adverse events (on the adverse event eCRF), constitutes a safety assessment.

## **10.2 Patient demographics/other baseline characteristics**

Baseline demographics and disease characteristics data will be listed and summarized for both first line and second line using the FAS and FAS-2L, as appropriate for the study and the Extension Phase. Qualitative data, such as gender, race, etc, will be presented by contingency type tables. Descriptive summary statistics (e.g. frequency, mean, median, range and standard deviation) will be used to present numeric data.

## **10.3 Treatments (study drug, concomitant therapies, compliance)**

### **10.3.1 Study medication**

Duration of study treatment exposure, cumulative dose and dose intensity will be summarized separately for each study treatment both in first line (everolimus and letrozole) and second line treatment (everolimus and exemestane), as appropriate for the core and the Extension Phase. The number of patients with dose changes/interruptions will be presented, along with reasons for the dose change.

### **10.3.2 Concomitant therapies**

Concomitant medications and significant non-drug therapies taken concurrently with the study drugs will be listed and summarized by Anatomical Therapeutic Chemical Classification System (ATC) term and preferred term by means of frequency counts and percentages. These summaries will include medications starting on or after the start of study treatment or medications starting prior to the start of study treatment and continuing after the start of study treatment. Concomitant medications will not be collected during the Extension Phase.

Any prior concomitant medications or significant non-drug therapies starting and ending prior to the start of study treatment will be listed.

The safety population will be used for all above mentioned concomitant medication tables and listings.

## **10.4 Primary objective**

The primary objective is to estimate the progression-free survival in patients treated with everolimus + letrozole in the first line setting.

### **10.4.1 Variable**

The primary efficacy endpoint in this study is PFS, defined as the time from the date of enrollment to the date of first documented progression or death due to any cause. If a patient has not had an event, PFS will be censored at the date of the last adequate tumor assessment. See RECIST, [Appendix 2](#). The primary efficacy endpoint will be assessed as per local radiological assessment.

### **10.4.2 Statistical hypothesis, model, and method of analysis**

The primary efficacy endpoint, PFS, will be analyzed based on the data from FAS. The median PFS as well as the 25th and 75 quartile will be estimated using the Kaplan-Meier method and presented along with 95% confidence intervals.

### **10.4.3 Handling of missing values/censoring/discontinuations**

In this study the primary analysis of PFS for first line treatment will be performed 12 months after the last patient's recruitment. The analysis of PFS for second line treatment will be performed 6 months later (18 months after the last patient's recruitment) provided that the number of patients in second line treatment is adequate for a reliable PFS analysis. Otherwise, this analysis will be performed 24 months after the last patient's recruitment. For the analyses, PFS will be censored on the date of last adequate tumor assessment, if no PFS event is observed before the cut-off date or before the date a new anti-neoplastic therapy or another investigational treatment for cancer is started, whichever occurs earlier. If a PFS event is observed after two or more missing or non-adequate tumor assessments, then the date of progression will be censored at the latest occurring evaluable tumor assessment. If a PFS event is observed after a single missing or non-evaluable tumor assessment, the actual date of event will be used.

## **10.5 Secondary objectives**

The secondary objective in this study is to determine the overall response rate and clinical benefit rate of everolimus + letrozole in the first line setting. Additionally, the median progression free survival and clinical benefit rate of everolimus + exemestane in 2nd line population will be evaluated. Additional secondary objectives are to evaluate the safety of everolimus + letrozole in the first line setting and to evaluate the safety of everolimus + exemestane in the second line setting. For the Extension Phase, the proportion of patients with clinical benefit will be reported and long term safety as assessed by the occurrence of AEs/SAEs will be evaluated.

The overall survival of patients treated with everolimus + letrozole in the first line setting will also be evaluated.

#### **10.5.1 Overall response rate and clinical benefit rate in first line**

Overall response rate (ORR) is defined as the proportion of patients with best overall response of complete response (CR) or partial response (PR) according to RECIST version 1.0 (see [Appendix 2](#)). Clinical benefit rate (CBR) is defined as the proportion of patients with best overall response of CR, PR or stable disease (SD) with a duration of 24 weeks or longer according to RECIST. ORR and CBR will be calculated based on the FAS, using local radiologist's/investigator's tumor assessment.

Patients with only non-measurable disease at baseline will be included in the numerator for ORR if they achieve a complete response and in the numerator for CBR if they achieve a complete response or stable disease lasting 24 weeks or longer. Proportions of subjects with ORR and CBR will be presented along with exact 95% confidence intervals ([Clopper and Pearson 1934](#)). The above analyses will also be repeated based on the data from subset of patients with only measurable disease at baseline.

#### **10.5.2 Progression free survival in second line**

Progression-free survival in the second line (PFS-2L) is defined as the time interval between start of 2nd line treatment and documented disease progression or death due to any cause reported during or after second-line treatment. The median PFS in the second line will be estimated using the Kaplan-Meier method and presented along with 95% confidence intervals.

#### **10.5.3 Overall response rate and clinical benefit rate in second line**

The analysis described in [Section 10.5.1](#) will be repeated on FAS-2L population to estimate the ORR and CBR of the second line study treatment.

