## 7.2 Assessment types

### 7.2.1 Efficacy assessments

#### Core Phase

Patients should have either at least one lesion that can be measured as per RECIST 1.0 criteria OR have bone lesions: lytic or mixed (lytic + sclerotic) in the absence of measurable disease as defined above.

For patients with measurable disease at baseline (as per RECIST 1.0 criteria), efficacy (overall tumor response and progression) will be evaluated every 8 weeks (+/- 1 week) during the Core Phase according to the RECIST 1.0 criteria. If an initial observation of response is made, a confirmation scan (or photography for measurable skin lesions) should be obtained at least 4 weeks after the initial observation. All patients being discontinued from the study for disease progression must have their progression documented using the criteria specified in [Appendix 2](#). All patients who discontinue study treatment for any reason (i.e., an adverse event, administrative reasons etc) other than disease progression or consent withdrawal will continue to have tumor assessments per the schedule during the Core Phase until disease progression or until new anti-cancer therapy is initiated.

All primary and secondary endpoints based on radiological (and photographic when applicable) assessments of tumor burden will be derived using the local (treating centers) radiologist's / investigator's assessment.

A bone scan or a skeletal survey should be performed at baseline for all patients within 28 days of enrollment. Any abnormalities (i.e., hotspots) identified on the bone scan must be confirmed by X-ray, CT scan with bone windows or MRI. Bone lesions identified at baseline should follow the same assessment schedule as for measurable lesions. Additional bone scans or skeletal surveys should be performed if clinically indicated. Abnormalities found on subsequent bone scans must also be confirmed by X-ray, CT scan or MRI.

The same method of assessment and the same technique should be used to characterize each identified and reported lesion at baseline for each study tumor assessment after start of study treatment.

If possible, each center should have a designated radiologist responsible for the interpretation of CT or MRI scans and the evaluation according to RECIST 1.0 criteria (see [Appendix 2](#) for details). The same radiologist/physician should perform the evaluation for the entire duration of the study. All radiology evaluations will be performed initially by the local radiologist.

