#### 14.2.8 Efficacy definitions

#### 14.2.9 Best overall response

The best overall response is the best response recorded from the start of the treatment until disease progression/recurrence (taking as reference for PD the smallest measurements recorded since the treatment started). In general, the patient's best response assignment will depend on the achievement of both measurement and confirmation criteria.

To be assigned a status of PR or CR, changes in tumor measurements must be confirmed by repeat assessments that should be performed not less than 4 weeks after the criteria for response are first met.

Longer intervals may also be appropriate. However, this must be clearly stated in the protocol. The main goal of confirmation of objective response is to avoid overestimating the response rate observed. In cases where confirmation of response is not feasible, it should be made clear when reporting the outcome of such studies that the responses are not confirmed.

The best overall response for each patient is determined from the sequence of overall (lesion) responses according to the following rules:

- CR = at least two determinations of CR at least 4 weeks apart before progression.
- PR = at least two determinations of PR or better at least 4 weeks apart before progression (and not qualifying for a CR).
- SD = at least one SD assessment (or better) > 6 weeks after randomization/start of treatment (and not qualifying for CR or PR).

The protocol should state if randomization or start of treatment is used as start date (baseline). This is then used in all definitions.

If a different minimum follow-up period is required to classify for overall response= 'stable disease', this must be specified in the protocol.

- PD = progression  $\leq$  12 weeks after randomization/ start of treatment (and not qualifying for CR, PR or SD).

If PD in a different follow-up period is considered overall response='progressive disease', this must be specified in the protocol.

The protocol should state if discontinuation due to 'Disease progression' or death due to study indication is considered PD even if this was not accompanied by documentation of PD based on tumor measurements. This depends on Phase of the study and the primary endpoint (e.g. Phase III studies in which progression-free survival is primary endpoint should consider only documented PD, whereas Phase I and II studies may consider all clinical deteriorations PD).

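### Second-line clinical benefit rate is a crude proportion over all FAS-2L although second-line entry stays open until the cut-off, so still-stable late starters count as failures and the rate is biased down by roughly 2 to 7 points

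*Protocol*

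**What the plan says.** - **Denominator.** Section 10.1.1 defines FAS-2L as a subset of the FAS, "which consists of all patients in the FAS who received at least one dose of" second-line medication. It sets no minimum follow-up.
- **Method.** Section 10.5.3 states that the Section 10.5.1 analysis "will be repeated on FAS-2L population to estimate the ORR and CBR of the second line study treatment". That analysis is a simple proportion with an exact (Clopper-Pearson) 95% interval.
- **CBR.** Section 10.5.1 defines it as "the proportion of patients with best overall response of CR, PR or stable disease (SD) with a duration of 24 weeks or longer".
- **ORR.** The same section defines it as "the proportion of patients with best overall response of complete response (CR) or partial response (PR) according to RECIST version 1.0", with no time condition. Appendix 2 (14.2.9) adds that confirmation "should be performed not less than 4 weeks after the criteria for response are first met". Under Section 7.2.1, tumours "will be evaluated every 8 weeks (+/- 1 week) during the Core Phase".
- **Entry to second line.** Sections 4.1 and 7.1.3 offer exemestane plus everolimus at first-line progression at any time in the Core Phase, to start within 28 days.
- **Timing.** Sections 4.1 and 10.4.3 set second-line PFS at 18 months after the last recruitment, "provided that the number of patients in second line treatment is adequate for a reliable PFS analysis", and otherwise at 24 months. No date is given for second-line ORR or CBR.

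**The concern.** In first line the crude 24-week proportion is sound. The primary analysis falls 12 months after the last recruitment, so every patient has had at least that much potential follow-up.

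Section 10.5.3 carries the method to a setting where this does not hold. Entry to second line does not close before the data are cut, so some patients cannot yet have 24 weeks of stable disease, however well they are doing. They are scored as non-benefit because of the calendar, not because of their disease or a missed scan.

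Second-line CBR is a stated secondary endpoint (Table 3-1). Its interval would be centred on too low a value, and the size of the error would depend on which cut-off is used. The condition in Section 10.4.3 concerns how many second-line patients there are, not how long they have been followed.

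**Working it through.** **1. The protocol's own figure.** The only design calculation is the CI table in Section 10.8: 200 patients, 18 months' recruitment (R), 12 months' further follow-up (F), 10% loss. With exponential PFS, λ = ln 2/median, and loss γ = −ln(0.9)/30 per month:

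D = 200 × λ/(λ+γ) × [1 − (e^(−F(λ+γ)) − e^(−(R+F)(λ+γ)))/(R(λ+γ))]; CI = median × exp(±1.96/√D).

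For medians of 11, 12, 13 and 14 months, D = 139.7, 133.8, 128.2 and 123.1. At 11 months, 11 × exp(±1.96/√139.7) = 9.32 to 12.98, as stated. The other three intervals also match to two decimals, so these inputs can be carried forward.

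**2. Share of FAS-2L starting under 24 weeks before the cut-off.** 24 weeks = 168/30.4375 = 5.52 months. Let U be the time from enrolment to cut-off, uniform on 18–36 months (18-month cut-off) or 24–42 months (24-month cut-off). Ignoring the delay of up to 28 days:

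share = E[e^(−λU)] × (e^(5.52λ) − 1)/(1 − E[e^(−λU)]).

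For median 11 and the 18-month cut-off: λ = 0.0630, E = 0.192, e^(5.52λ) − 1 = 0.416, so share = 0.192 × 0.416/0.808 = 9.9%. For median 14 it is 11.7%. At 24 months the shares are 6.3% and 7.9%. A simulation that includes the delay gives 10.3%, 12.1%, 6.5% and 8.2%.

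**3. Effect on CBR.** The protocol gives no second-line planning value. As an assumption, take the second-line median PFS as 3.2, 5.5 or 7.8 months. The end values are the local-assessment medians of the two arms of the phase III trial described in Section 1.2.1.4. Take benefit as second-line PFS of at least 24 weeks: CBR = exp(−ln 2 × 5.52/median) = 30%, 50% or 61%. If first- and second-line PFS are independent, the reported rate is CBR × (1 − share), so shortfall = CBR × share. Simulated results (CBR with full follow-up → CBR on all FAS-2L, in %):

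| First-line median | Cut-off | Share | 2L median 3.2 | 2L median 5.5 | 2L median 7.8 |
|---|---|---|---|---|---|
| 11 | 18 months | 10.3% | 30.2 → 27.1 | 49.8 → 44.7 | 61.2 → 54.9 |
| 14 | 18 months | 12.1% | 30.2 → 26.5 | 49.9 → 43.8 | 61.2 → 53.8 |
| 11 | 24 months | 6.5% | 30.3 → 28.3 | 49.8 → 46.5 | 61.2 → 57.2 |
| 14 | 24 months | 8.2% | 30.3 → 27.8 | 49.9 → 45.8 | 61.2 → 56.2 |

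The shortfall is 3.1–7.4 points at 18 months and 2.0–5.0 points at 24 months.

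**4. Crediting early responders.** If 24 weeks qualifies stable disease only, and 25–50% of benefiting patients have a confirmed CR or PR by 12 weeks, the shortfall falls to about 2–6 points (18 months) and 1.5–4 points (24 months).

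**5. ORR.** With a first scan at 8 weeks and confirmation at least 4 weeks later, possibly only at the 16-week scan, only starts in roughly the last 12–16 weeks lack time for a confirmed response.

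**6. Check against reported counts.** The Amendment 5 rationale reports 202 enrolled, with 64 on first line and 19 on second line at the June 2016 (18-month) cut-off. FAS-2L was then at most 202 − 64 = 138, so the 19 were at least 19/138 = 14% of it. Patients whose 24-week status was open lie essentially among those 19, plus any who stopped without progression and were still being scanned.

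**The case against.** Counting undetermined patients as failures is a common, conservative convention, and rules for them often sit in the SAP. The second-line rate is descriptive, with no test or threshold, so a downward bias cannot create a false efficacy claim. At a rate of 50% the exact interval has a half-width of about 9 points with 138 patients and 11 with 80, which exceeds the bias. Kaplan-Meier PFS-2L (Section 10.5.2) already handles the same censoring.

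Most of this bears on weight. It does not remove the point. The protocol does fix the set and the method, and following them as written produces the bias. The cause is the cut-off, not missing assessments. The Kaplan-Meier curve does not correct the CBR that is reported.

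Four stronger readings are tempting and not supported:
- **ORR suffers likewise.** It has no 24-week criterion, and no ORR bias has been quantified here.
- **The documents set 18 or 24 months for CBR.** They set those dates for second-line PFS only; the CBR date is open.
- **All late starters, or all 19 ongoing patients, are misclassified.** Those who progress before 24 weeks are true failures, and some of the 19 will already have passed 24 weeks.
- **The affected share is as high as 15%.** That needs a first-line median near 22 months, against the 11–14 planned.

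**Conclusion.** The point stands for second-line CBR. As written, the estimate is biased down by roughly 2–7 points: about 3–7 at an 18-month cut-off and 2–5 at 24 months, somewhat less if early confirmed CR or PR counts at once. ORR is exposed only at the margin, and first-line CBR is unaffected.

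The size rests on assumptions: uniform 18-month accrual, exponential PFS, a first-line median of 11–14 months, a borrowed second-line range, and independence between lines. Positive correlation between lines makes the gap a little larger. Accrual was in fact late-loaded: the Amendment 3 rationale reports 56 enrolled by 17 March 2014, so 202 − 56 = 146 entered in the last nine months. That also pushes the share up rather than down.

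The direction is certain and the size modest. The repair is worth making because it is cheap, not because a conclusion of the trial hangs on it.

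**What to change.** In Section 10.5.3:
1. State that second-line ORR and CBR are analysed at the 24-month cut-off, where fewer patients are affected.
2. Keep the all-FAS-2L proportion. Beside it, report CBR among patients whose second-line start is at least 25 weeks before the cut-off (24 weeks plus the one-week scan window), whatever their outcome. A Kaplan-Meier 24-week estimate is an acceptable alternative.
3. Report how many patients have an undetermined 24-week status.
4. Do not apply the 25-week restriction to ORR, where it would discard evaluable responders.

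**Cost.** A few sentences, no new data, and about 7–12% fewer patients in the restricted estimate, with a slightly wider interval. The restriction is not a complete cure. Late starters are those who did well longest in first line, so leaving them out tilts the set towards early progressors. With no correlation between lines the bias goes. At a correlation of 0.3–0.5 the restricted CBR stays about 1–3 points low (for example 42.6% against 45.3%). This is why both estimates should be shown.
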